## **8.1 PRETREATMENT EVALUATION**

### Screening

- Informed Consent

### Pre-Treatment Evaluation

- History and physical exam
- TUR or biopsy of bladder tumor (within 60 days of treatment initiation)
  - Urine cytology will be included with this TURBT whenever possible.

## **9.1 TREATMENT/INTERVENTION PLAN**

Patients enrolled in the study will receive 6 consecutive intravesical BCG treatments. After the 3 month follow-up cystoscopy appointment, patients will undergo another set of 6 intravesical BCG treatments. Each set of BCG treatments will include 6 injections within a recommended 6 weeks, a regimen that is within the standard of care. Any delay of treatment will be allowable per standard of care BCG treatment procedures. Such disruptions may include but are not limited to unforeseen circumstances, institutional holidays, or patients's schedule.

## **9.2 BCG suspension and administration procedures**

Study participants will undergo intravesical treatment with approximately  $1$  to  $8 \times 10^8$  CFU of BCG (1 vial), which is equivalent to approximately 50 mg (wet weight), lyophilized (freeze-dried) powder.

The suspension will be prepared using aseptic technique. The steps are as follows:

1. Draw 1 mL of sterile saline (0.9% sodium chloride injection USP) at 4° to 25° into a small syringe (e.g., 3 mL) and resuspend 1 vial of BCG.
2. Resuspend 1 vial of BCG by gently swirling until a homogenous suspension is obtained. Avoid forceful agitation, as this may cause clumping of the mycobacteria.
3. Dispense the cloudy suspension into the top end of a catheter-tip syringe that contains 49 mL of saline diluent, bringing the total volume to 50 mL.
4. Gently invert the syringe to mix.

Administration:

1. Place a small gauge (i.e., 14fr) Foley catheter and empty the patient's bladder of any residual urine.
2. Instill the 50 mL of resuspended BCG into the bladder through the Foley catheter.
3. Remove the Foley catheter.
4. The patient will be instructed not to urinate for a minimum of 1 hour.

### **9.3 Monitoring and compliance**

The treatment will be instilled in an outpatient MSKCC facility by a trained professional. After each treatment, the patient will be assessed for toxicity. If patients experience toxicity between the scheduled visits, they will be instructed to contact their physician's office for further instruction, assessment, or treatment.

Intravesical BCG does not have systemic interactions.

## **10.0 EVALUATION DURING TREATMENT/INTERVENTION**

3 months (+/- 4 weeks) after initiation of therapy

- Urine cytology
- Cystoscopy
- TUR will be scheduled (at physician's discretion)

6 months (+/- 4 weeks) after initiation of therapy

- Urine cytology
- Cystoscopy
- TUR will be scheduled (at physician's discretion)

Evaluation	Pretreatment screening	3 months (+/- 4 weeks) after initiation of therapy	6 months (+/- 4 weeks) after initiation of therapy
History and physical	x		

Urine cytology	X	X	X
Cystoscopy		X	X
Trans-urethral resection tumor*	X (within 60 days of treatment initiation)	X (*will be scheduled at physician's discretion)	X (*will be scheduled at physician's discretion)

## 11.1 TOXICITIES/SIDE EFFECTS

- At each follow-up visit, enrolled patients will be evaluated for toxicities and side effects due to therapy. As is standard of care a Nursing Treatment/Assessment form will be used to record any toxicities and side effects. A research assistant will follow the patient and maintain a record of toxicities and side effects that are possibly, probably or definitely related to protocol therapy and will be documented on the CTCAE toxicities form and collected for data entry. Only toxicities that are considered Grade >2, per CTCAE version 4.0 will be captured for this trial.
- Clinically insignificant symptoms/findings of expected symptoms listed below that may be collected in the Nursing Treatment/Assessment form will not be graded or attributed on the toxicities forms.
  - Symptoms of bladder irritability, which are related to the inflammatory response that is induced by BCG, include urgency and frequency of urination, cystitis, nocturia, and pelvic pain. Symptoms occur in approximately 60% of patients receiving intravesical BCG. Symptoms are usually treated with symptomatic control using medicines such as propantheline bromide, oxybutynin chloride, and acetaminophen. Symptoms are not related to dose.
  - Hematuria is another potential side effect that is also related to the inflammatory response induced by BCG. This occurs in approximately 25% of patients treated with BCG and is usually self-limiting.
  - “Flu-like” symptoms (malaise, fever, and chills) often reflect hypersensitivity reactions to BCG. These symptoms occur in approximately 33% of patients and can be treated symptomatically with medicines such as antihistamines and acetaminophen.
  - The following adverse events were reported in ≤1% of patients: anemia, BCG sepsis, coagulopathy, contracted bladder, diarrhea, epididymitis/prostatitis, hepatic granuloma, hepatitis, leukopenia, neurologic (unclassified) symptoms, orchitis, pneumonitis, pyuria, rash, thrombocytopenia, urethritis, and urinary obstruction.

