### **3.6 Rationale**

1. The standard care for patients with high-risk non-muscle-invasive bladder cancer who do not respond to BCG treatment is radical cystectomy. Surgery with radical cystectomy is associated with a complication rate of up to 60%, as well as with poor self-image owing to external urine collecting devices. There is a need for a more efficient non-surgical approach for patients with these tumors.
2. The current treatment regimen of 6 intravesical treatments with BCG is arbitrary. The proposed study will test the efficacy of a new regimen of BCG treatments.

3. The proposed study will attempt to define the acceptable clinical toxicity profile of intravesical BCG.
4. There is a need to increase the durability of the response to intravesical BCG; the treatment regimen in the proposed study will attempt to address this.
5. The proposed study will incorporate recent data that provided new insight into the T cell activity in response to BCG therapy. Furthermore, we will focus on the idea that priming the immune system will result in a more robust immunologic response against any tumor that is present.

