### **13.0 CRITERIA FOR REMOVAL FROM STUDY**

If at any time the patient develops progressive disease or experiences an unacceptable toxicity, the patient will be referred to receive standard treatment. An unacceptable toxicity is defined as severe frequency, dysuria or pain. Patients that cannot tolerate BCG instillations and refuse due to side effects are also defined as unacceptable toxicity. These patients will be evaluable for the primary endpoint of the study.

Patients with progressive disease will be considered to have experienced treatment failure, and patients with toxicities will have their outcomes ascertained 6 months after the initiation of the first BCG treatment. The number of patients, who do not complete therapy, and the reasons for not completing therapy, will be included in the final study report.

If at any time the patient is found to be ineligible for the protocol as designated in the section on Criteria for Patient/Subject Eligibility (i.e., a change in diagnosis), the patient will be removed from the study.

Patients who are removed from the study due to withdrawal of consent or who are lost to follow-up will not be considered evaluable and will be replaced.

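### A non-serious BCG toxicity of Grade 2 or lower that delays or ends treatment need not be graded or attributed in the trial data

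*Combined protocol and SAP*

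**What the plan says.** Section 11.1 limits the trial's toxicity data in two ways. Events go on the CTCAE form for data entry only if they are judged at least possibly related to therapy, and a grade limit applies as well: "Only toxicities that are considered Grade >2, per CTCAE version 4.0 will be captured for this trial". Expected symptoms regarded as clinically insignificant are not graded or attributed. The wider record is the standard-of-care nursing document: "a Nursing Treatment/Assessment form will be used to record any toxicities and side effects". Section 9.3 adds: "After each treatment, the patient will be assessed for toxicity".

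Section 13.0 defines treatment-ending toxicity without a CTCAE grade. It says "An unacceptable toxicity is defined as severe frequency, dysuria or pain", and then "Patients that cannot tolerate BCG instillations and refuse due to side effects are also defined as unacceptable toxicity". It requires the final report to give the number of patients who do not complete therapy and their reasons. Patients who withdraw consent or are lost to follow-up are not evaluable and are replaced.

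On delays, Section 9.1 says "Any delay of treatment will be allowable per standard of care BCG treatment procedures" and gives open-ended examples: "Such disruptions may include but are not limited to unforeseen circumstances, institutional holidays", and the patient's schedule. Toxicity is not among the examples, and no reason has to be recorded.

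Section 3.6 lists as a rationale item: "The proposed study will attempt to define the acceptable clinical toxicity profile of intravesical BCG". The objectives in Section 2.1 are the response rate and progression to muscle-invasive disease. Section 14.0 contains no toxicity summary.

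**The concern.** The new element of this regimen is a second course, giving 12 instillations where current care gives 6. A reader of the results will want to know whether patients could tolerate the added course and what limited it. Persistent symptoms of modest grade can be enough to make a patient postpone or decline an instillation. Section 13.0 recognises this by counting refusal because of side effects as unacceptable toxicity whatever the grade.

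Under the Section 11.1 rule, a patient can meet that definition and still have no graded, attributed toxicity in the trial data. A patient who is delayed by symptoms and then completes both courses may not appear in any required report. Descriptive information on tolerability is at stake. The efficacy conclusion is not.

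**Working it through.** The plan states no figure on this point, so the check is to follow each kind of BCG-related event through the sections and see what the text requires.

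| Related event | Trial toxicity data (11.1) | Other route | What is not required |
|---|---|---|---|
| Grade 3 or higher | Graded, attributed, entered | Nursing form | Any link to a delay it caused |
| Serious, Grade 2 or lower | Not captured | Serious-event report with grade and relationship (17.3) | Nothing material here |
| Non-serious, Grade 2 or lower, patient refuses or stops BCG | Not captured | Stop counted and reason reported (13.0); nursing form | Prospective grade and attribution |
| Non-serious, Grade 2 or lower, BCG delayed and then completed | Not captured | Nursing form only; 9.1 asks for no reason | Grade, attribution, and any report of the delay |
| Non-serious, Grade 2 or lower, treatment unchanged | Not captured | Nursing form | Left out by design; not at issue |

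The third and fourth rows hold the gap.

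- **Refusals and stops.** The event itself is not lost. Section 13.0 brings the count and the reason into the final report. It does not ask for a CTCAE grade or a relatedness category.
- **Delays followed by completion.** These fall outside the Section 13.0 report, which concerns non-completion. No other section brings them in, so this is the stronger half of the point.
- **Timing.** Toxicity is assessed after each treatment, the nursing form records it, and Section 16.1 says source documentation will be available. The instillation concerned should therefore be retrievable.

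**Can the gap be sized?** Section 11.1 gives approximate symptom rates, and Section 14.0 sets 75 patients with a completed second cystoscopy:

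- bladder irritability: 0.60 × 75 = 45
- flu-like symptoms: 0.33 × 75 = 24.75, about 25
- hematuria: 0.25 × 75 = 18.75, about 19

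These counts show only that symptoms are common. The documents do not split the rates by grade and do not say how often symptoms alter treatment. The groups can also overlap. No estimate of the number of affected patients follows.

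**The case against.** The strongest reply is that the Grade >2 limit is an open and legitimate choice for a small single-arm study, and that most of what matters is covered elsewhere. Stops and their reasons are reported, serious events carry grade and relationship, and the nursing form holds the rest. Toxicity appears only in the rationale, where nothing says that low-grade events must be graded. The clause on clinically insignificant symptoms suggests that Section 11.1 aims to leave out trivial complaints, and an event that ends treatment is hard to call trivial. The case report forms are not among the documents, so dates of delays and reasons for them may be collected after all.

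Much of this stands. It limits the point to grade and attribution, plus delays, and it keeps confidence in a practical loss at medium. It does not remove the point. Whatever the clause on insignificant symptoms intends, the grade sentence still excludes a treatment-limiting event of Grade 2 or lower. The plan does not provide for going back to the nursing record, and grading or attributing events afterwards may be less reliable than doing so at the time.

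Two stronger readings are tempting. One is that Sections 11.1 and 13.0 contradict each other. They do not: one sets what is entered as toxicity data and the other sets when a patient leaves treatment, so different thresholds are compatible. The other is that patients who stop for toxicity disappear from the results. Section 13.0 keeps them evaluable, with outcome ascertained at 6 months, and reports why they stopped.

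**Conclusion.** The point holds as a minor, inexpensive improvement to data collection, with medium confidence. Followed as written, Section 11.1 allows a non-serious related toxicity of Grade 2 or lower to delay or end BCG without being graded or attributed in the trial data, and no section requires toxicity-related delays followed by completion to be reported.

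A reader might infer that the response result is biased or that a stated objective cannot be met. The documents support neither. The analysis set and the response definition do not depend on toxicity capture, and toxicity is not a listed objective.

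The conclusion assumes that the case report forms ask for no more than the text does. If they already collect the reason for each delay and the grade of any toxicity behind a delay or stop, only the wording of Section 11.1 needs to change.

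**What to change.** In Section 11.1, keep the Grade >2 threshold in general and add one exception. Any related toxicity, of whatever grade, that leads to a delay, refusal or stop of BCG is graded, attributed and entered from the existing nursing form, with the instillation number.

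Report these events descriptively among all patients who received at least one instillation. That denominator is needed because Section 13.0 replaces patients who withdraw consent or are lost to follow-up, and some of them may already have been treated.

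The cost is modest extra data entry by the research study assistant already assigned under Section 16.1, and one short descriptive summary. No new visit or procedure is needed, since toxicity is already assessed after each treatment. The change concerns only what is recorded and reported; it proposes no rule for delaying or stopping BCG.

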## 12.0 CRITERIA FOR THERAPEUTIC RESPONSE/OUTCOME ASSESSMENT

Patient response/outcome will be assessed by both urine cytology and cystoscopy at 6 months after initiation of therapy.

Patients who have a response are those who have no evidence of disease in their bladder by both urine cytology and cystoscopy.

Patients whose disease remains at the same stage or is downstaged without complete resolution are considered nonresponders and will be documented as having recurred. Any positive result for either cystoscopy or cytology exam will be followed by TURBT at the physician's discretion.

Patients with worsening tumor, defined as the upstaging from non-muscle invasive to muscle invasive disease, or metastatic disease will be documented as disease progression.

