### 4.3 Intervention

**Rationale:** The current regimen of 6 intravesical instillations of BCG for high risk superficial bladder cancer is arbitrary. No randomized trials have been performed to identify the optimal number of intravesical BCG instillations needed to obtain the lowest recurrence rates.

**Treatment Plan:** Patients with high risk superficial bladder cancer will be treated with 2 induction courses (12 intravesical instillations total) of BCG. Patients will undergo a diagnostic TUR which will include a urine cytology when possible to evaluate their bladder tumor/tumors, a past TURBT and urine cytology within 60 days of treatment initiation will also suffice. If the pathological characteristics of the tumors result in the patient being deemed eligible, they will be asked to enroll in the study. A prior/current history and physical examination will also be evaluated. After the first induction course (6 intravesical instillations) of BCG, patients will be scheduled for a cystoscopy at 3 months (+/- 4 weeks). During this 3 month cystoscopy appointment patients will again submit a urine cytology prior to the procedure. If worsening tumor is found a TURBT will be scheduled at the physicians discretion. All enrolled patients will be evaluated for the primary endpoint, as defined in section 14.0, of the study, regardless of whether they received the full course of treatment.

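### A patient positive at 3 months and clear at 6 can count as a responder, while the audit rate that appears to supply the 66% null counts such patients as failures, and no planned output shows how many there are

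*Combined protocol and SAP*

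**What the plan says.** Section 12.0 fixes the time of assessment, "Patient response/outcome will be assessed by both urine cytology and cystoscopy at 6 months after initiation of therapy", and defines response: "Patients who have a response are those who have no evidence of disease in their bladder by both urine cytology and cystoscopy". Neither sentence requires a clear examination at 3 months.

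Three other provisions bear on a patient who is positive at 3 months:

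- Section 9.1 gives the second course without conditions: "After the 3 month follow-up cystoscopy appointment, patients will undergo another set of 6 intravesical BCG treatments".
- Section 10.0 lists, at both the 3-month and the 6-month visit, "TUR will be scheduled", at the physician's discretion.
- Section 13.0 names one fixed failure: "Patients with progressive disease will be considered to have experienced treatment failure". Section 12.0 defines progression as upstaging to muscle-invasive disease, or metastatic disease.

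Section 14.0 sets the uninteresting rate at 66% or less and the rate of interest at 80% or more. The regimen is declared effective with at least 52 responders among 75 patients. The section gives no source for the 66% but refers the reader to Section 3.0 for the design and its rationale. Section 3.3 reports an institutional audit of 1021 patients treated with BCG: 140 had no response at 3 months, 205 had none at 6 months, and the two groups combined gave 34% treatment failure at 6 months.

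Besides the response count, the planned outputs are the 6-month progression rate with its confidence interval (Section 14.0) and the number of patients not completing therapy, with reasons (Section 13.0).

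**The concern.** The trial has one arm, so its conclusion rests on comparing the observed response count with 66%. That comparison is fair only if the trial and the source of the 66% classify the same patient the same way.

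They appear not to. Take a patient with Ta high-grade disease at the 3-month cystoscopy who is resected or observed, receives course 2, and is clear at 6 months. The trial can count this patient as a responder. The audit composite counts the same patient as a failure because of the 3-month result.

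The difference runs in one direction. A rule that ignores a non-progressive 3-month positive can only give the same count as the stricter rule or a higher one. Clearing between 3 and 6 months may reflect course 2, a resection, or both. None of the planned outputs shows 3-month status or on-study TURBT among responders, so a reader of the final report could not see how far the conclusion depends on these patients.

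**Working it through.** **Inputs.** Audit counts 140, 205 and 1021 (Section 3.3); null 0.66, target 0.80, n = 75, cutoff 52, type I error 0.05 and type II error 0.20 (Section 14.0).

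**1. Where the 66% appears to come from.** (140 + 205)/1021 = 345/1021 = 33.8%, the audit's 34%. Its complement is 66.2%. The plain sum reproduces the 34%, so the two groups are added without overlap and every 3-month non-responder is a failure.

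**2. The audit on the trial's rule.** Section 3.3 does not say how many of the 140 were clear at 6 months. If none were, 6-month-only response is (1021 − 345)/1021 = 66.2%. If all were, it is (1021 − 205)/1021 = 79.9%. A like-for-like null could lie anywhere between, and the upper end is almost the 80% target.

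**3. How many trial patients.** 140/1021 = 13.7%, and 0.1371 × 75 = 10.3 patients expected. The binomial 95% range at that rate is 5 to 16. This is an expected number, not a ceiling: the trial may also enrol previously BCG-treated patients (Section 1.0), whose 3-month rate is not given. In the other direction, any of the 140 who progressed would be failures in the trial too.

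**4. Effect on the decision (illustration).** Let f be the share of 3-month-positive patients who are clear at 6 months with no true gain from course 2. The documents give no value for f. The response rate with no gain is then p = 0.66 + 0.1371 × f, and the chance of declaring success is the exact binomial tail with n = 75.

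At f = 0 the stated cutoff of 52 gives a type I error of 31.7% and, at 80% response, power of 99.0%. It does not reproduce the stated 0.05 and 0.20, which is a separate problem. To isolate the present point, a hypothetical cutoff of 57 is shown beside it. That is the smallest cutoff at n = 75 that holds type I error below 0.05 (4.1%, against 6.9% at 56).

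| f | p | Expected patients converted (10.3 × f) | P(X ≥ 57), hypothetical | P(X ≥ 52), as stated |
|---|---|---|---|---|
| 0 | 0.660 | 0 | 4.1% | 31.7% |
| 0.15 | 0.681 | 1.5 | 8.6% | 46% |
| 0.25 | 0.694 | 2.6 | 13.2% | 56% |
| 0.50 | 0.729 | 5.1 | 32% | 79% |

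Under either cutoff, a handful of converted patients raises the false-positive chance materially. If course 2 causes part of the clearing, the bias is smaller.

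**The case against.** The strongest defence is that the endpoint fits the stated aim. The objective is response to 12 instillations at 6 months, and the 3-month visit falls in the middle of the regimen. A patient who is positive after 6 instillations and clear after 12 may be exactly the benefit sought. This stands, and it is why the 6-month rule should remain primary.

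Second, the audit may be a fair benchmark for one course. Section 3.6 gives radical cystectomy as standard care for BCG non-responders. If many of the 140 moved on to other treatment, they had no comparable 6-month bladder result. That is possible and would place the like-for-like null near 66%, but Section 3.3 does not say, so the range stays open.

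Third, the Section 12.0 sentence "Patients whose disease remains at the same stage or is downstaged without complete resolution are considered nonresponders and will be documented as having recurred" has no visit attached and could be read to cover 3 months. It follows the 6-month sentence, however, and nothing in the plan carries a 3-month positive forward as a failure.

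Fourth, the 3-month data are collected anyway, so the count could be derived later. It could, but without pre-specification reporting it is optional and can be decided once the result is known.

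A reader might also infer that the plan lets surgery manufacture responders. The documents do not support that. The 3-month TUR is discretionary, and every resected patient may also receive course 2. Section 4.3 offers little support: "If worsening tumor is found a TURBT will be scheduled at the physicians discretion" may concern only progressors, since Section 12.0 defines worsening tumor as progression, and progressors are failures. The Section 12.0 statement "Any positive result for either cystoscopy or cytology exam will be followed by TURBT", again at the physician's discretion, may apply only at 6 months. The resection route rests on Section 10.0.

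**Conclusion.** The concern holds as a mismatch between the endpoint and its apparent benchmark, combined with a gap in the planned reporting. On the natural reading of Sections 9.1, 10.0, 12.0 and 13.0, a patient with non-progressive disease at 3 months who is clear at 6 can count as a responder. The audit composite matching the 66% null counts such a patient as a failure. The comparison therefore favours declaring the regimen effective.

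Two assumptions carry this. One is that the 66% comes from the audit; the arithmetic and the pointer to Section 3.0 support it, but the plan does not say so. The other is that some 3-month positives would clear by 6 months without benefit from course 2; the documents give no share. The size of the bias is therefore unknown.

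A reader might infer that the true null is about 80%, or that at most 10 patients are affected. Neither follows. The first needs all 140 audit non-responders to have been clear at 6 months, and the second treats an expected number as a maximum. The primary analysis need not be replaced, but it cannot be interpreted safely without the missing count.

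**What to change.** Keep the 6-month rule as primary. In Section 14.0, pre-specify:

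- (a) A supportive response count on the same patients that treats any positive cystoscopy or cytology at 3 months as nonresponse, whether or not the patient was resected, compared with 66%. List patients with no 3-month result separately.
- (b) The number of primary responders who were positive at 3 months, and how many of them had an on-study TURBT before the 6-month assessment.
- (c) An interpretation rule. If the primary count meets the protocol's success cutoff (the corrected one, if it is revised) and the supportive count does not, the report states that the conclusion depends on patients positive at 3 months and clear at 6, without attributing this to surgery alone.

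The cost is one paragraph and one table, built from the cystoscopy and cytology already scheduled in Section 10.0 and TURBT dates in the patient record. No visits or patients are added. The drawback is that the supportive count gives course 2 no credit for late clearing. It also matches the audit only approximately, since Section 3.3 does not say how 3-month non-response was judged. It should therefore stay supportive. Aligning the TURBT trigger across Sections 4.3, 10.0 and 12.0 would be a minor clarification, not part of this point.
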